**12.2. Appendix 2: Schedule of Activities**

**12.2.1. Protocol Defined Schedule of Events**

Procedure	Screening V1 (up to 30 days before Day 1)	V2 Day -9	Treatment Period (13 weeks)							Follow-up  V9 (42 days post last dose)	Notes
			V3 Baseline Day 1	V4 Day 14	V5 Day 28	V6 Day 56	V7 Day 80	V8 Last dose 90	Unscheduled visit 		
Visit window (days)	- 30 to -11	-11 to -7	-2 to day 1	12 - 16	24 - 32	52- 60	76 - 84	85 - 91		126- 140	There should be an attempt to conduct all assessments for a visit within a single day  .
Informed consent	X										Obtained prior to performing any study-related procedures.
Inclusion and exclusion criteria	X										
Demography/ medical/medication/ drug/ alcohol history/ PD disease staging	X										
Full physical examination	X								X	X	
Brief physical exam			X	X	X	X		X			
12-lead ECG	X		X	X	X	X		X	X	X	
Vital signs	X		X	X	X	X		X	X	X	
HIV, Hepatitis B and C screening	X										If test otherwise performed within 3 months prior to first dose of study treatment, testing at screening is not required

Procedure	Screening V1 (up to 30 days before Day 1)	V2 Day -9	Treatment Period (13 weeks)							Follow- up  V9 (42 days post last dose)	Notes	
			V3 Baseline Day 1	V4 Day 14	V5 Day 28	V6 Day 56	V7 Day 80	V8 Last dose 90	Unscheduled visit 			
Hepatitis C viral RNA PCR										X		If evidence of Hepatitis C antibodies at screening visit, then Hepatitis C viral RNA PCR required to exclude active infection. This sample is not needed if Hepatitis C screening is negative.
Haematology (Full blood count)/ Clinical Chemistry (Creatinine, urea and electrolytes, liver function tests, glucose)	X		X	X	X	X			X	X	X	Participants should fast overnight for at least 8 hours prior to collection of these samples.
HbA1c	X								X			
hsCRP, Fibrinogen			X						X		X	
25-OH Vitamin D Total, 25-OH Vitamin D2, 25-OH Vitamin D3	X								X		X	
Lipid panel	X		X	X	X	X			X		X	
Genetic sample			X									Obtain after participant is randomized. Informed consent to obtain the genetics sample must be obtained before collecting a sample.
Pharmacokinetic sampling				X 	X 	X 			X 	X		Times of dose administration for the two doses immediately preceding a PK sample should be accurately recorded.
Reproductive Tissue Biomarkers			X		X	X			X		X	
PSA	X		X		X	X			X		X	For male participants only
Bone Biomarkers			X			X			X		X	

Procedure	Screening V1 (up to 30 days before Day 1)	V2 Day -9	Treatment Period (13 weeks)							Follow-up  V9 (42 days post last dose)	Notes
			V3 Baseline Day 1	V4 Day 14	V5 Day 28	V6 Day 56	V7 Day 80	V8 Last dose 90	Unscheduled visit 		
Exploratory Biomarkers			X	X	X	X		X		X	
Urinalysis	X		X					X	X	X	
DXA			X		X	X		X	X	X	
Spirometry	X		X			X		X			Follow ATS/ ERS guidelines [Celli, 2004] and Quanjer reference equation [Quanjer, 2012].
Sniff Nasal Inspiratory Pressure	X		X			X		X			
Leg strength	X		X		X	X		X		X	
Handgrip strength	X		X					X			
Short Physical Performance Battery	X		X		X	X		X		X	
Incremental Shuttle Walk Test		X	X					X			Practice incremental shuttle walk test conducted at day -9
Endurance Shuttle Walk Test			X					X			
COPD Assessment Test			X			X		X			
St George Respiratory Questionnaire COPD (SGRQ-c)			X					X			
Patient Global Rating of Severity			X					X			
Patient Global Impression of Change				X	X	X		X		X	
Daily PROactive Physical Activity in COPD instrument and Physical Activity Monitor	X	X 				X	X 				Physical activity monitor dispensed at screening, day -9, day 56 and day 80 visits. Activity monitor should be worn for 7 days at each timepoint and returned at the next visit.
Monitored home exercise program		X	X	←=====→				X			Participants will receive training for the exercise program at Day -9, and will formally begin exercises on day 1
Patient exit interview										X	

Procedure	Screening V1 (up to 30 days before Day 1)	V2 Day -9	Treatment Period (13 weeks)							Follow-up  V9 (42 days post last dose)	Notes	
			V3 Baseline Day 1	V4 Day 14	V5 Day 28	V6 Day 56	V7 Day 80	V8 Last dose 90	Unscheduled visit 			
Randomization			X								All Baseline assessments must be obtained prior to randomization.	
Study treatment provided to participant			X		X	X					The subject should take their first dose of study treatment in the clinic after randomization.	
Study treatment			X	←=====→				X			Participants should dose study treatment in the clinic at each clinic visit during the treatment period.	
Study treatment accountability by study site			X	X	X	X		X			The required counting of pills by site staff to check compliance is not considered redispensing the study medication.	
AE review			X	←=====→							X	
SAE review			X	←=====→							X	
Concomitant medication review			X	←=====→							X	
Optional sub-study measures												
Cardiac and liver MRI (additionally prostate MRI in males)			X 					X 			MRI is an optional assessment undertaken at participating centres only.	

ECG= Electrocardiogram; HIV= Human Immunodeficiency Virus; PK= Pharmacokinetic; PSA= Prostate Specific Antigen; DXA= Dual-energy X-ray Absorptiometry; AE= Adverse Event; SAE= Serious Adverse Event.

1. An unscheduled clinic visit may occur at any time if the investigator believes an unscheduled visit is clinically warranted. Individual listed assessments are optional and are performed as needed to follow unresolved findings of clinical concern. Note: The “Unscheduled visit” case report form (CRF) form should be completed as soon as possible following the Unscheduled visit.

2. As stated in [Section 8.2](#), if a participant decides to withdraw or is withdrawn by the responsible physician, the reasons for withdrawal and the results of any relevant tests will be recorded in the CRF and the planned safety follow-up procedures will be performed, where possible. These include physical examination, 12-lead ECG, vitals, blood tests, urinalysis and concomitant medication review as listed for the follow-up visit (V9).
3. Attempt to conduct all visits within a single day however the baseline (day 1) and last dose (day 90) visits may require subjects to visit the study centre on more than one day in order to complete MRI and DXA scans, and possibly other assessments. These scans, and any other assessments, should be conducted within the specified visit window, and prior to randomization at the baseline visit. Further details on the suggested order of assessments will be given in the SRM.
4. Take PK sample prior to dosing in the clinic
5. Take PK sample 1-4 hours post-dose (sites should try and ensure that a range of times are sampled within this time window for different participants, i.e. all PK samples should not be taken at 1 hour post dose or 2 hours post dose).
6. Take PK sample 5-8 hours post-dose (as above, sites should try and ensure that a range of times are sampled within this time window for different participants).
7. At V3 Baseline Day 1 and V8 Last dose 90, the patients will return the Daily PROactive Physical Activity in COPD Instrument and the Physical Activity Monitor to the site. Patients will not be dispensed the Daily PROactive Physical Activity in COPD Instrument and the Physical Activity Monitor at the end of these visits.
8. All MRI Scans (Cardiac MRI, Liver MRI and, if applicable, Prostate MRI) should preferably be scheduled on the same day. Acquisition of the Cardiac MRI should be prioritized above the other two scans if it becomes unfeasible to perform all the MRI scan.

The following points must be noted:

- If assessments are scheduled for the same nominal time, THEN the assessments should occur in the following order:
  - i. vital signs
  - ii. 12-lead ECG
  - iii. blood draws.

Note: The timing of the assessments should allow the blood draw to occur at the time specified in the SoA.

## 12.3. Appendix 3: Assessment Windows

### 12.3.1. Definitions of Assessment Windows for Analyses

Analysis Set / Domain	Parameter (if applicable)	Protocol Window		Target	Analysis Window		Analysis Timepoint
		Beginning Timepoint	Ending Timepoint		Beginning Timepoint	Ending Timepoint	
All	All	Day -30	Day -11	Day -30 to -11	Day -60	Day -12	Screening/Visit 1
All	All	Day -11	Day -7	Day -9	Day -11	Day -5	Visit 2
All	All	Day -2	Day 1	Day 1	Day -4	Day 1	Visit 3, Day 1
All	All	Day 12	Day 16	Day 14	Day 10	Day 18	Visit 4, Day 14
All	All	Day 24	Day 32	Day 28	Day 22	Day 34	Visit 5, Day 28
All	All	Day 52	Day 60	Day 56	Day 50	Day 62	Visit 6, Day 56
All	All	Day 76	Day 84	Day 80	Day 76	Day 84	Visit 7, Day 80
All	All	Day 85	Day 91	Day 90	Day 85	Day 97	Visit 8, Day 90
All	All	Day 126	Day 140	Day 132	Day 126	Day 140	Follow-Up, Day 132

- For scheduled visits the analysis visit would equal the nominal visit irrespective of the assessment date and irrespective of whether that date falls in the visit window.
- Only unscheduled visits are slotted according to the table above and this slotting algorithm will be applicable for both efficacy and safety domains.
- After slotting of Un-scheduled visits, if there are multiple assessments at a planned timepoint, then the value closest to the target day for that window will be considered. If the multiple assessments are equidistant from the target day, then mean of the assessments will be considered.
- For any time post baseline and baseline (if the definition of baseline is the latest pre-dose visit) all assessments are used irrespective of whether they fall into visit windows or not.

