ECG= Electrocardiogram; HIV= Human Immunodeficiency Virus; PK= Pharmacokinetic; PSA= Prostate Specific Antigen; DXA= Dual-energy X-ray Absorptiometry; AE= Adverse Event; SAE= Serious Adverse Event.

1. An unscheduled clinic visit may occur at any time if the investigator believes an unscheduled visit is clinically warranted. Individual listed assessments are optional and are performed as needed to follow unresolved findings of clinical concern. Note: The “Unscheduled visit” case report form (CRF) form should be completed as soon as possible following the Unscheduled visit.
2. As stated in Section 8.2, if a participant decides to withdraw or is withdrawn by the responsible physician, the reasons for withdrawal and the results of any relevant tests will be recorded in the CRF and the planned safety follow-up procedures will be performed, where possible. These include physical examination, 12-lead ECG, vitals, blood tests, urinalysis and concomitant medication review as listed for the follow-up visit (V9).
3. Attempt to conduct all visits within a single day however the baseline (day 1) and last dose (day 90) visits may require subjects to visit the study centre on more than one day in order to complete MRI and DXA scans, and possibly other assessments. These

scans, and any other assessments, should be conducted within the specified visit window, and prior to randomization at the baseline visit. Further details on the suggested order of assessments will be given in the SRM.

4. Take PK sample prior to dosing in the clinic
5. Take PK sample 1-4 hours post-dose (sites should try and ensure that a range of times are sampled within this time window for different participants, i.e. all PK samples should not be taken at 1 hour post dose or 2 hours post dose).
6. Take PK sample 5-8 hours post-dose (as above, sites should try and ensure that a range of times are sampled within this time window for different participants).
7. At V3 Baseline Day 1 and V8 Last dose 90, the patients will return the Daily PROactive Physical Activity in COPD Instrument and the Physical Activity Monitor to the site. Patients will not be dispensed the Daily PROactive Physical Activity in COPD Instrument and the Physical Activity Monitor at the end of these visits.

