3.3.1. Risk Assessment

Potential Risk of Clinical Significance	Summary of Data/Rationale for Risk	Mitigation Strategy
Investigational Product (IP) GSK2881078		

Elevation of Alanine Aminotransferase (ALT) and other liver function tests (AST, bilirubin, total and direct).
	
This has been observed in a variety of SARMs and was observed (minimal) in the 14-day and 13-week rat toxicity studies with administered GSK2881078.
 
One subject had elevations of Liver Function Tests (LFTs) in Phase 1a, but it was unclear if this was related to drug. Transient elevations in ALT without concomitant changes in bilirubin were observed in Phase 1b.
	
Monitoring of liver function tests will be in place at all clinic visits. This study will use follow up procedure that were used in Phase I of development of GSK2881078 for participants who have met liver stopping criteria, as detailed in Section 8.1.1 of this protocol.

Effects on reproductive organs/tissues:
 
Men – testes, epididymis, and prostate gland
 
Women – ovaries and uterus
	
These are recognized effects of SARM pharmacology and show recovery on discontinuation of dosing.
 
Test article-related organ weight and/or microscopic changes were observed in the gonads and other associated reproductive tissues in rat 14-day and 13-week toxicity studies administered GSK2881078. All test article-related microscopic findings were reversible after a 4- or 8- week off dose period. Test article-related effects were observed in male mating, fertility, gonadal function, and male-mediated development in a male rat fertility study.
 
In phase I studies, all male subjects dosed with
	
Males with PSA levels >4.0 ng/mL will be excluded.
 
Females will be post-menopausal.
 
Participants will be monitored at baseline, Day 28, Day 56, Day 89 and follow-up for changes in the following levels:
 
 • luteinizing hormone • follicle stimulating hormone • testosterone • free testosterone (calculated) • estradiol

Potential Risk of Clinical Significance	Summary of Data/Rationale for Risk	Mitigation Strategy

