Note: The confidence interval for odds ratio (GSK2881078/Placebo) is calculated using the Exact method.

Programming note: continue for the next visit and repeat for Sex: Male.

for the treatment. In case of violation of the assumptions, the same model is fitted with log of ratio to baseline and replacing the covariate baseline with log baseline.

[2] GSK2881078-Placebo.

Example : EFF\_T8  
Protocol: XXXXXXXX  
Population: Analysis

Table XX  
Descriptive Summary of Patient Global Impression of Change

Sex: Female

Visit	Treatment	N	n	PGIC Category						
				Much Worse	Worse	Slightly Worse	No Change	Slightly Better	Better	Much Better
Day 14	GSK2881078	xx	xx	xx (xx.x%)	xx (xx.x%)	xx (xx.x%)	xx (xx.x%)	xx (xx.x%)	xx (xx.x%)	xx (xx.x%)
	Placebo	xx	xx	xx (xx.x%)	xx (xx.x%)	xx (xx.x%)	xx (xx.x%)	xx (xx.x%)	xx (xx.x%)	xx (xx.x%)
Day 28	GSK2881078	xx	xx	xx (xx.x%)	xx (xx.x%)	xx (xx.x%)	xx (xx.x%)	xx (xx.x%)	xx (xx.x%)	xx (xx.x%)
	Placebo	xx	xx	xx (xx.x%)	xx (xx.x%)	xx (xx.x%)	xx (xx.x%)	xx (xx.x%)	xx (xx.x%)	xx (xx.x%)
....										

Note: The percentages have been calculated based on n.

Programming note: Continue with Visit= Day 56, Day 90 and then repeat for Sex: Male

Example : EFF\_T9  
Protocol: XXXXXXXX  
Population: Analysis

Table XX  
Descriptive Summary of Patient Global Rating of Severity

Sex: Female  
Treatment: Placebo

Analysis Visit	N	n	PGRS Category				
			None	Mild	Moderate	Severe	Very Severe
Baseline	xx	xx	xx (xx.x%)	xx (xx.x%)	xx (xx.x%)	xx (xx.x%)	xx (xx.x%)
	xx	xx	xx (xx.x%)	xx (xx.x%)	xx (xx.x%)	xx (xx.x%)	xx (xx.x%)
Day 90	xx	xx	xx (xx.x%)	xx (xx.x%)	xx (xx.x%)	xx (xx.x%)	xx (xx.x%)
	xx	xx	xx (xx.x%)	xx (xx.x%)	xx (xx.x%)	xx (xx.x%)	xx (xx.x%)

....

Programming note: repeat for Sex: Male

Listings

Example : EFF\_L1  
 Protocol: XXXXXX  
 Population: Analysis

Listing XX  
 Listing of Leg Press Strength (kg) Results

Sex: Female  
 Treatment: XXXXX

Site Id/ Unique Subject Id	Visit / Analysis Visit	Assessment Date/Day	Parameter	Leg Press Performed? (if no, provide reason)	Assessment Value	Change/Percent Change from Baseline
	Unscheduled / Visit X Day	DDMMYY/1	Number of Successful Lifts	Yes	xx	xxxx / xxx.x
				No		
			Starting Lift Weight (Unit)	Yes	xx (xxx)	xxxx / xxx.x
			Last Successful Lift 1-RM (Unit)	No		

Note: Baseline value will be the latest pre-dose assessment with a non-missing value, including those from unscheduled visits.

Programming note: Sorted by treatment, Center, Subject, Visit and continue for SEX: Male  

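### In by-visit safety summaries an unscheduled repeat can displace the scheduled value, so which value represents a visit depends partly on the result

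*SAP*

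**What the plan says.** SAP 12.3.1 handles the two kinds of visit differently. A scheduled assessment stays with its planned visit: "For scheduled visits the analysis visit would equal the nominal visit irrespective of the assessment date". An unscheduled one is placed by date: "Only unscheduled visits are slotted according to the table above and this slotting algorithm will be applicable for both efficacy and safety domains". Once both sit in the same visit, "if there are multiple assessments at a planned timepoint, then the value closest to the target day for that window will be considered". For ties, "If the multiple assessments are equidistant from the target day, then mean of the assessments will be considered".

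SAP 12.5.2 (Unscheduled Visits) and 12.6.1 (Multiple Measurements at One Analysis Time Point) repeat the rule, and 12.5.2 confirms that slotted unscheduled values enter the by-visit summaries. The nominal-visit sentence settles which visit a scheduled value belongs to. It does not say that this value wins over a slotted one, and neither does any other sentence.

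On why unscheduled assessments take place, footnote 1 of the protocol's Schedule of Activities says: "Individual listed assessments are optional and are performed as needed to follow unresolved findings of clinical concern". Protocol 9.5.4 adds that clinically significant laboratory abnormalities are to be repeated until they normalise, return to baseline or are no longer judged significant.

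Two provisions limit the reach of the rule. Any-time post-baseline derivations use every assessment (SAP 12.3.1), and listings show scheduled and unscheduled values together (SAP 12.5.2).

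**The concern.** A nearest-to-target rule is neutral only if the existence of a second value does not depend on the first. Here it largely does. A participant whose scheduled result is unremarkable will usually have one value in the window. A participant whose result is abnormal is likely to have a second, and that one may represent the visit. When repeats regress or resolve, the by-visit mean loses part of the abnormality, and it loses more in the arm with more abnormalities.

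Safety is a primary objective with no formal comparisons (protocol 10.3.2, SAP 2.4), so the descriptive tables carry the evidence. The by-visit displays of chemistry (including glucose), haematology, ECG and vital signs are the exposed ones, for example Tables 3.15, 3.18, 3.30 and 3.32. The protocol's risk table gives a reason to care about short-lived changes: "Transient elevations in ALT without concomitant changes in bilirubin were observed in Phase 1b". A transient rise is the kind of finding that a later repeat could displace.

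**Working it through.** The plan states no figure for this rule, so there is none to reproduce. Two checks were made.

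**1. How often a later repeat displaces the scheduled value.**

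Inputs: visit windows, target days and analysis windows from the table in SAP 12.3.1. For repeat gaps, Appendix 4 of the protocol gives 2-3 days to the first return for ALT from 5 to below 8xULN, and weekly for ALT from 3 to below 5xULN. Assumption: every in-window scheduled day and every gap counts equally.

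Let *T* be the target day, *s* the scheduled day and *g* the gap, so the repeat falls on *s* + *g*. The repeat is strictly nearer when |*s* + *g* − *T*| < |*s* − *T*|. For a later repeat this requires *s* < *T* and *g* < 2(*T* − *s*). It ties when *g* = 2(*T* − *s*). A scheduled value taken on or after the target day is never displaced by a later repeat.

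| Visit (protocol window) | *g* = 2 or 3: replaced + averaged | Share | *g* = 7 |
|---|---|---|---|
| Day 14 (12-16) | 2 + 1 | 3/10 | 0/5 |
| Day 28 (24-32) | 6 + 1 | 7/18 | 1/9 |
| Day 56 (52-60) | 6 + 1 | 7/18 | 1/9 |
| Day 90 (85-91) | 8 + 1 | 9/14 | 2/7 |

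For example, at Day 90, scheduled days 85 to 88 give 2(*T* − *s*) = 10, 8, 6 and 4. All exceed 3, so both gaps replace (8 combinations). Day 89 gives 2, which ties at *g* = 2 and is kept at *g* = 3. Days 90 and 91 are kept. With *g* = 7, replacement needs *T* − *s* of at least 4: days 85 and 86 at Day 90, day 24 at Day 28, day 52 at Day 56, and none at Day 14. Day 90 is the most exposed visit because its target lies near the end of its window.

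Each replacement in an arm of 25 moves that arm's visit mean by 1/25 = 4% of the gap between the two values.

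**2. What this could do to a between-arm difference.**

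The documents give no repeat rates or variances, so this is a simulation on assumed inputs: normal outcome with SD 1; active-minus-placebo shift 0.5 or 1.0 SD; 5% or 10% of placebo values abnormal; within-participant correlation 0.5 or 0.7; scheduled day uniform over the protocol window; one repeat 1-3 days later, only if the scheduled value is abnormal; 1,000,000 participants per arm.

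- Days 28 and 56: the by-visit difference shrinks by 2.3% to 4.7%.
- Day 90: it shrinks by 4.0% to 7.5%. With shift 1.0 SD, placebo rate 5% and correlation 0.5, the difference falls from 1.00 to 0.93 SD, and the proportions abnormal at the visit go from 5.0% versus 26.0% to 2.5% versus 17.3%.
- No treatment shift (Day 90): no between-arm bias.
- Repeats that worsen by an assumed 0.8 SD (Day 90, shift 1.0 SD, rate 5%, correlation 0.7): the difference grows from 1.00 to 1.07 SD.

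If the scheduled value is kept whenever present, displacement is zero and the difference returns to the assumed shift.

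**The case against.** Several objections have force.

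- **Direction.** A reader might infer that by-visit means are simply biased towards normal in the active arm. The documents do not establish that. Repeats can worsen, as the last simulated case shows. Footnote 1 also allows an unscheduled visit at any time it is clinically warranted, so an abnormal symptom-driven value on Day 29 would displace a normal scheduled value on Day 32 (1 day from target against 4). Protocol section 9 also permits repeats for technical sample problems, which need not follow an abnormal result.
- **Primary endpoint.** A reader might infer that leg press is affected, because "this slotting algorithm will be applicable for both efficacy and safety domains" and the leg-press listing shell has a row "Unscheduled / Visit X Day". That row is template text. It recurs in the shells for both shuttle walks, CAT, SGRQ, SnIP, handgrip and MRI, none of which is in the unscheduled column of the Schedule of Activities. Leg strength is not there either. DXA is, but nothing suggests that scans are repeated because of their result.
- **Lipids and hormones.** The unscheduled column also omits lipids, reproductive biomarkers, PSA and HbA1c, so Table 3.26 and Figures 3.3 and 3.4 (glucose apart) are weak examples.
- **Detection.** A reader might infer that abnormalities vanish from the report. They do not. Maximum-grade, maximum-QTc and worst-case displays (Tables 3.16, 3.19, 3.29, 3.31, 3.33; Figures 3.1 and 3.2) and the listings keep them.
- **The existing rule** is mechanical and does not look at treatment, whereas any exception for unusable samples adds a judgement in a study with an unblinded sponsor team.

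These points limit the reach and certainty of the concern. They do not supply a reason for letting a result-triggered repeat stand in for the scheduled value in a by-visit table.

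**Conclusion.** The concern holds for by-visit summaries of chemistry (including glucose), haematology, ECG and vital signs. There, the value that represents a visit depends in part on whether the scheduled result prompted a repeat. The expected direction is an understatement of abnormalities in the arm that has more of them, conditional on repeats tending to regress or resolve.

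The size is probably modest. The date counts rest on equal weighting of days and on two Appendix 4 intervals, and the percentage shrinkage rests wholly on assumed variances, shifts and repeat behaviour. The primary leg-press analysis is little exposed, and worst-case, any-time and listing displays are unaffected. This is a low-cost improvement to the SAP and does not threaten the trial's conclusions.

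**What to change.** In SAP 12.3.1, 12.5.2 and 12.6.1, state that for by-visit summaries a non-missing scheduled value represents its visit. An unscheduled value is slotted only when the scheduled value is missing, or was recorded by the laboratory or site as not analysable, without reference to treatment. The nearest-to-target and tie rules then apply only among unscheduled values. All values stay in the worst-case, any-time post-baseline and listing displays, and the baseline definition in SAP 5.2 is unchanged.

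The cost is one sentence in three places and a small derivation change. The downside is small: an off-target scheduled value will sometimes be used when a repeat lies nearer the target. The SAP already accepts off-target scheduled values, since it assigns them by nominal visit whatever their date.
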